SPECIFIC RISKS AND PROTECTION MEASURES

1. Fluoroscopic Procedures

As with every clinical study, there may be some risks. However, doses of radiation exposure received will be much lower than those known to produce detectable health effects. Previously reported literature shows that fluoroscopy-based procedure (angiography) on the lower limb result in a typical effective dose of 0.83 mSv per min (0.083 rem per min) (Verdun¹). Mettler, et al. have reported that the typical effective dose for a conventional knee procedure is 0.005 mSv (0.0005 rem)². According to either estimate, the additional risk of a fluoroscopic procedure involving the knee ranges between "Negligible" to "Low" for a 2 minute exam (Verdun). A previous fluoroscopy TKA study conducted at another hospital with a 2 minute on-time limit shows that the average effective dose was 0.14 mSv (0.0014 rem) with a maximum dose of 0.27 mSv (0.027 rem). The additional risk for all subjects in this previous study would be considered "Negligible." To account for subject variability and differences in imaging techniques, all subjects enrolled in this study will receive less than 2.0 rem. 2.0 rem is considered "Low" risk. It is unlikely that anyone in this study will approach the 2.0 rem limit. Since the fluoroscopy data will be collected in one session, there will only be one day in which the participants will be exposed to this amount of radiation.

2. CT Scan

In addition to the radiation exposure from the fluoroscopy procedure, all subjects will be exposed to radiation from the CT scan of the knee (which is considered an "extremity"), estimated at 0.01 rem, according to the American Nuclear Society's Radiation Dose Chart,

<http://www.ans.org/pi/resources/dosechart/> (Attachment 4). The radiology department at Porter Adventist hospital uses a software program call Caredose that automatically keeps the dose as low as possible on all CT exams. Insofar as the amount of time for the CT scans taking place, we estimate approximately 30 minutes for the exam itself.

In conclusion, a participant who will be fluoroscoped for less than two minutes will be exposed to a maximum amount of only 2.0 rems of radiation. This means that the maximum total exposure rate will be less than 2.0 rems per subject for the entire experiment. The participant's knee joint will be fluoroscoped using negligible to low risk levels of radiation according to published literature.

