Abdomen	8	80	0.25	20.0
Lower limbs	6	50	0.10	5.0

Source.—Adapted from reference 27.

*Including image acquisition.

Table 3
Generic Dose-Length Products, Conversion Factors, and Effective Doses at CT in a Standard Adult Patient

Examination	Dose-Length Product (mGy • cm)	Conversion Factor (mSv/mGy • cm)	Effective Dose (mSv)
Head	1000	0.0023	2.3
Neck	400	0.0054	2.2
Chest	300	0.017	5.1
Abdomen-pelvis	500	0.015	8.0
Lower limbs (excluding pelvis)	500	0.0012	0.6

Sources.—References 21 and 32.

Table 4
What to Tell Your Patients concerning Additional Risk of Death from Cancer

Effective Dose (mSv)	Risk	Quantification	Examination
<0.1	$<10^{-6}$	Negligible	Radiography of the chest (postero-anterior), extremities, or teeth
0.1–1.0	10^{-5}	Minimal or extremely low	Abdomen, lumbar spine
1.0–10	10^{-4}	Very low	CT of the brain, chest, or abdomen
10–100	10^{-3}	Low	Multiphase CT
>100	$>10^{-2}$	Moderate	Interventional procedures,* repeat CT

Sources.—References 10 and 22.

*Including the deterministic effects of ionizing radiation (skin burns).

ATTACHMENT 2

Mettler, et al. "Effective Doses in Radiology and Diagnostic Nuclear Medicine." *Radiology* 248.1 (2008): 254-263. <http://radiology.rsna.org/content/248/1/254.full.pdf+html>

Results

Representative values and ranges of effective doses reported in the literature for various examinations and procedures are presented in Tables 1-3.

In addition to effective dose, absorbed organ doses are important for some procedures that either involve high doses or include sensitive tissues in the primary radiation beam. For CT scanning, organs in the beam can receive doses that are 10-100 mGy but are usually in the range of 15-30 mGy per single CT sequence (162-169).

Doses to the lens of the eye during CT scanning of the head have been reported to be 30-50 mGy (170-174). Values depend on whether the lens is in the direct beam or out of the beam when the gantry is angled. Angulation of the gantry for head CT studies can reduce the eye dose by 90%, to about 3-4 mGy. For many new scanners, such as portable intensive care unit scanners, positron emission tomography/CT scanners, and dual-tube multidetector CT scanners, the gantry cannot be angled, which will result in higher eye doses when head CT examinations are performed.

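### Do the inconsistent dose pair, the risk word and the 2.0 rem total in the radiation-risk section call for a change to the plan?

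*Protocol*

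**What the plan says.** The text is in the Protocol under Specific Risks and Protection Measures, item 1 (Fluoroscopic Procedures) and item 2 (CT Scan).

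- **Prior study.** For an earlier knee-replacement study with the same two-minute limit, item 1 reports that "the average effective dose was 0.14 mSv (0.0014 rem) with a maximum dose of 0.27 mSv (0.027 rem"). The sentence that begins "The additional risk for all subjects in this previous study would be considered" then assigns the word Negligible.
- **Cited estimates.** Item 1 cites 0.83 mSv per minute (lower-limb angiography) and 0.005 mSv (a conventional knee procedure). It continues "According to either estimate, the additional risk of a fluoroscopic procedure involving the knee ranges between" Negligible and Low for a two-minute examination.
- **Limit.** Item 1 also says that every enrolled subject will receive under 2.0 rem, that this level counts as Low, and that nobody is likely to come near it.
- **CT.** Item 2 opens "In addition to the radiation exposure from the fluoroscopy procedure, all subjects will be exposed to radiation from the CT scan of the knee", classes the knee as an extremity and takes 0.01 rem from Attachment 4.
- **Conclusion.** The closing paragraph says that "a participant who will be fluoroscoped for less than two minutes will be exposed to a maximum amount of only 2.0 rems of radiation". It goes on: "This means that the maximum total exposure rate will be less than 2.0 rems per subject for the entire experiment".

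The risk words come from Attachment 1, Table 4: Negligible below 0.1 mSv, "Minimal or extremely low" for 0.1 to 1.0, Very low for 1.0 to 10, and Low for 10 to 100.

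**The concern.** Three statements cannot be reproduced from the section's own figures. One mSv/rem pair contradicts the other three. The word Negligible is applied to all subjects of a study whose maximum, "with a maximum dose of 0.27 mSv (0.027 rem"), is outside the tabled band for that word. And a limit on fluoroscopy alone cannot yield the same limit for fluoroscopy plus CT.

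This would matter because participants are exposed to radiation with no intended direct benefit, so this section carries the justification. If an error here hid a dose near the limit, or moved this trial's participants into a higher risk category, the protocol would have to be corrected before anyone was exposed.

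**Working it through.** **Step 1: unit pairs.** Inputs are the four pairs in item 1.

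| mSv | rem | mSv / rem |
|---|---|---|
| 0.83 (per min) | 0.083 (per min) | 10 |
| 0.005 | 0.0005 | 10 |
| 0.14 | 0.0014 | **100** |
| 0.27 | 0.027 | 10 |

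The 0.83 figure reproduces from Attachment 1, Table 2 (lower limbs): 5.0 mSv / 6 min = 0.833 mSv per minute. Only the 0.14 pair fails. At 10 mSv per rem, 0.14 mSv would be 0.014 rem, and 0.0014 rem would be 0.014 mSv. The documents do not show which member is mistyped.

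**Step 2: risk words against Table 4.**

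- Prior-study maximum: 0.27 mSv lies in 0.1 to 1.0, so Negligible does not fit. The units of this pair agree, so the result does not depend on step 1.
- Prior-study average: 0.14 mSv falls in the same band; 0.014 mSv would be Negligible.
- Two-minute estimate: 2 × 0.83 = 1.66 mSv, Very low. This lies inside the protocol's stated range of Negligible to Low.
- Limit: 2.0 rem = 20 mSv, Low, as the protocol says.

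**Step 3: the total.** The CT figure is 0.01 rem = 0.1 mSv, which matches the 10 mrem extremity entry in Attachment 4. As a range check, the differently labelled lower-limb row of Attachment 1, Table 3 gives 500 × 0.0012 = 0.6 mSv = 0.06 rem.

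If 2.0 rem covers fluoroscopy only, the formal bound is 2.0 + 0.01 = 2.01 rem, or 2.0 + 0.06 = 2.06 rem. That is 20.1 or 20.6 mSv, still Low. If 2.0 rem covers everything a subject receives, the stated total is consistent.

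**Step 4: sums from documented doses.**

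| Fluoroscopy (mSv) | + CT 0.1 | + CT 0.6 |
|---|---|---|
| 0.014 (average, if the rem figure holds) | 0.114 | 0.614 |
| 0.14 (average, if the mSv figure holds) | 0.24 | 0.74 |
| 0.27 (prior-study maximum) | 0.37 | 0.87 |
| 1.66 (two minutes at the cited rate) | 1.76 | 2.26 |

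The largest sum is 2.26 mSv = 0.226 rem, and 20 / 2.26 = 8.8. To bring the total to 20 mSv with the protocol's CT figure, two minutes of fluoroscopy would have to deliver (20 − 0.1) / 2 = 9.95 mSv per minute. That is 9.95 / 0.83 = 12 times the cited rate.

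**The case for a change.** The strongest case for a change is that risk text for a study without intended benefit should be exactly reproducible, and that correcting it costs a few words. The unit pair and the label are wrong on the page, and the inference in the conclusion does not follow from the sentence before it. All of that stands as an editorial observation.

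The rest carries less weight.

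- The wrong pair and the wrong word describe another study's subjects. For its own participants the protocol gives a range up to Low, and every documented estimate lies at or below that level.
- The 2.0 rem limit can be read as study-wide: item 1 words it as what each enrolled subject will receive, and the conclusion comes after the CT text and speaks of the whole experiment. The opposite reading is also open, because the limit stands under the fluoroscopy heading and the conclusion argues from fluoroscopy time. This is an ambiguity of wording.
- The figure of 2.01 rem adds a CT estimate to a ceiling that nobody is expected to approach. It is not an expected dose.
- Placing the upper end at Low when the two-minute estimate is Very low errs on the cautious side.
- The choice of the extremity CT figure is already explained in item 2, with its source attached.

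**Conclusion.** Two clerical slips are confirmed: one mSv/rem pair inconsistent by a factor of 10, direction unknown, and one risk word a band too low for a prior-study maximum of 0.27 mSv against a bound of 0.1 mSv. A third sentence leaves open whether 2.0 rem covers fluoroscopy alone or fluoroscopy plus CT. The difference is 0.01 rem, 0.5% of the limit (3% with the Table 3 figure), and does not alter the category.

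These passages should be reconciled with their source whenever the protocol is next edited, but that is proofreading and does not change the plan. The comparison of braced and unbraced gait, the measurement of medial condylar separation and the tests in the SAP make no use of these figures. The two-minute fluoroscopy limit and the 2.0 rem limit do not rest on the faulty pair or label.

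The conclusion assumes that the cited doses represent this site's equipment. They are typical values, not bounds, but the margin is about ninefold against the largest sum. The protocol also has fluoroscopy on-time and any available machine output recorded for each subject. The consent pages were not available, so whether they repeat these figures could not be checked.

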- A representative from JointVue will be present at data collection to acquire 3 dimensional bone images using JointVue's ultrasound procedure and software. This individual will sign a pledge of confidentiality.

Clinical Observations:

There are no clinical observations made during this data collection or from the images obtained through data collection. UT researchers do not require any kind of report from the radiology

department. Unless the data collection site requires such a report, there will be no radiology report generated for this procedure conducted as a result of this study. Therefore, no RT will review such a report for the procedures, which would be the only way such a "significant problem" would be determined. No data will be returned to the physician's office for evaluation or review. However, if researchers see anything in the imaging that is extremely out of the ordinary (e.g., floating body, severe dislocation, potential tumors [spots of incredibly dense tissue on bones and skin]), they will bring this to the attention of Drs. [name] or [name] or their staff.

It is not anticipated that the imaging collected during this study would potentially provide benefit to specific subjects by influencing the physician's treatment plan.

BENEFITS

The potential benefits from this study include, but are not limited to:

- Better understanding of the joints analyzed with the same technique in the past.
- Future brace design improvements based on the kinematic findings.
- There is no intention of any direct benefit to participants of the study. Information related to the data gathered may be provided to Drs. [name] or [name] by the researchers if something out of the ordinary is seen during the imaging. However, researchers are not radiologists and cannot interpret anything they may see. If there is something within the imaging that is obviously wrong as mentioned above, then this could result in potential modification of a subject's treatment plan if images collected as a result of this study reveal any kind of "significant problem."

COMPENSATION

The participants in this study will receive a \$50 onetime payment in the form of a check for participation that will be mailed to the participant after completion of their CT Scan.

METHODS TO OBTAIN "INFORMED CONSENT" FROM PARTICIPANTS

Informed consent will be obtained prior to any procedures being conducted. Subjects who are agreeable to participate will be scheduled to visit Porter Adventist Hospital on the day that UT researchers will travel there for data collection. Appointed staff from Colorado Joint Replacement and/or UT researchers will be responsible for consenting the participants, giving them ample time to review and complete the forms and assist the participants with review of the documentation, if the participants are unable to read the form on their own. Only upon signed consent will the subject be allowed to participate in the study. If the subject chooses to be removed from the study after participating, his/her video, fluoroscopy footage and ultrasound data that was collected will be managed according to the subject's response on the Revocation of Consent form. A copy of his/her Revocation of Consent will be attached to his/her IC and placed in a separate, secure file for IRB review. These consent forms will be stored at UT, Knoxville and will be accessible by only the aforementioned personnel.

Drs. [name] and [name] will not be present during the consenting process to avoid possible subject coercion to participate. Subjects may contact Colorado Joint Replacement with any questions they may have.

From previous studies, we have determined that it takes approximately 15 minutes to consent a subject and answer any questions that s/he may have. We have also estimated approximately 20 minutes for researchers to guide the subject through the steps of the procedure, allow the subject

to practice the activity and then to actually perform the activity under fluoroscopic surveillance; actual radiation exposure will be up to, but not more than two minutes. The ultrasound portion of the data collection should take approximately 10 minutes. We have estimated a total time of approximately 45 minutes for each subject to be consented and complete the fluoroscopy and ultrasound procedures.

ATTACHMENT 1

Table 2
Generic Dose-Area Products, Conversion Factors, and Effective Doses at Angiography in a Standard Adult Patient

Examination*	Fluoroscopy time (min)	Dose-Area Product (Gy • cm ²)	Conversion Factor (mSv/Gy • cm ²)	Effective Dose (mSv)
Cerebrum	12	75	0.04	3.0
Coronary arteries	4	75	0.20	15.0
Abdomen	8	80	0.25	20.0
Lower limbs	6	50	0.10	5.0

Source.—Adapted from reference 27.

*Including image acquisition.

Table 3
Generic Dose-Length Products, Conversion Factors, and Effective Doses at CT in a Standard Adult Patient

Examination	Dose-Length Product (mGy • cm)	Conversion Factor (mSv/mGy • cm)	Effective Dose (mSv)
Head	1000	0.0023	2.3
Neck	400	0.0054	2.2
Chest	300	0.017	5.1
Abdomen-pelvis	500	0.015	8.0
Lower limbs (excluding pelvis)	500	0.0012	0.6

Sources.—References 21 and 32.

Table 4
What to Tell Your Patients concerning Additional Risk of Death from Cancer

Effective Dose (mSv)	Risk	Quantification	Examination
<0.1	$<10^{-6}$	Negligible	Radiography of the chest (postero-anterior), extremities, or teeth
0.1–1.0	10^{-5}	Minimal or extremely low	Abdomen, lumbar spine
1.0–10	10^{-4}	Very low	CT of the brain, chest, or abdomen
10–100	10^{-3}	Low	Multiphase CT
>100	$>10^{-2}$	Moderate	Interventional procedures,* repeat CT

Sources.—References 10 and 22.

*Including the deterministic effects of ionizing radiation (skin burns).

ATTACHMENT 2

Mettler, et al. "Effective Doses in Radiology and Diagnostic Nuclear Medicine." *Radiology* 248.1 (2008): 254-263. <http://radiology.rsna.org/content/248/1/254.full.pdf+html>

Results

Representative values and ranges of effective doses reported in the literature for various examinations and procedures are presented in Tables 1-3.

In addition to effective dose, absorbed organ doses are important for some procedures that either involve high doses or include sensitive tissues in the primary radiation beam. For CT scanning, organs in the beam can receive doses that are 10-100 mGy but are usually in the range of 15-30 mGy per single CT sequence (162-169).

Doses to the lens of the eye during CT scanning of the head have been reported to be 30-50 mGy (170-174). Values depend on whether the lens is in the direct beam or out of the beam when the gantry is angled. Angulation of the gantry for head CT studies can reduce the eye dose by 90%, to about 3-4 mGy. For many new scanners, such as portable intensive care unit scanners, positron emission tomography/CT scanners, and dual-tube multidetector CT scanners, the gantry cannot be angled, which will result in higher eye doses when head CT examinations are performed.

Radiation dose to the breast tissue is of critical importance, especially in girls and young women. Chest CT scanning results in relatively high doses to breast tissue. Doses have been estimated to be 20-60 mGy for a CT examination performed for pulmonary embolism, 50-80 mGy for a CT coronary angiography examination, and even 10-20 mGy to the inferior part of the breast for an abdominal CT examination (175-177). Even though lower x-ray energies are used, as a comparison, for mammography, the American College of Radiology and the Mammography Quality Standards Act of 1992 regulations require that the mean glandular dose for a single mammogram to a normal-sized breast with 50% glandularity be less than 3 mGy.

Discussion

As mentioned earlier, effective dose is a calculated age- and sex-averaged value

that is used as a robust measure to compare detriment from cancer and hereditary effects due to various procedures involving ionizing radiation. Martin (178) has pointed out a number of limitations in its use, including about $\pm 40\%$ uncertainty for a reference patient. Often, effective dose is calculated and expressed to a much greater precision

than is warranted, and we have expressed values to only one significant digit. There clearly are additional problems in trying to apply the sex-averaged effective dose to procedures that predominantly involve one sex (such as mammography).

The sources of information reviewed were variable in quantity, qual-

Table 1

Adult Effective Doses for Various Diagnostic Radiology Procedures

Examination	Average Effective Dose (mSv)	Values Reported in Literature (mSv)
Skull	0.1	0.03-0.22
Cervical spine	0.2	0.07-0.3
Thoracic spine	1.0	0.6-1.4
Lumbar spine	1.5	0.5-1.8
Posteroanterior and lateral study of chest	0.1	0.05-0.24
Posteroanterior study of chest	0.02	0.007-0.050
Mammography	0.4	0.10-0.60
Abdomen	0.7	0.04-1.1
Pelvis	0.6	0.2-1.2
Hip	0.7	0.18-2.71
Shoulder	0.01	...
Knee	0.005	...
Other extremities	0.001	0.0002-0.1
Dual x-ray absorptiometry (without CT)	0.001	0.001-0.035
Dual x-ray absorptiometry (with CT)	0.04	0.003-0.06
Intravenous urography	3	0.7-3.7
Upper gastrointestinal series	6*	1.5-12
Small-bowel series	5	3.0-7.8
Barium enema	8*	2.0-18.0
Endoscopic retrograde cholangiopancreatography	4.0	...

*Includes fluoroscopy.

Table 2

Adult Effective Doses for Various CT Procedures

Examination	Average Effective Dose (mSv)	Values Reported in Literature (mSv)
Head	2	0.9-4.0
Neck	3	...
Chest	7	4.0-18.0
Chest for pulmonary embolism	15	13-40
Abdomen	8	3.5-25
Pelvis	6	3.3-10
Three-phase liver study	15	...
Spine	6	1.5-10
Coronary angiography	16	5.0-32
Calcium scoring	3	1.0-12
Virtual colonoscopy	10	4.0-13.2

ATTACHMENT 3

PS010-3

HEALTH
PHYSICS
SOCIETY

RADIATION RISK IN PERSPECTIVE POSITION STATEMENT OF THE HEALTH PHYSICS SOCIETY[†]

Adopted: January 1996

Revised: July 2010

Further revised: May 2016

Contact: [name]
Executive Director
Health Physics Society
[contact]
[contact]
Email: [contact]
<http://www.hps.org>

The Health Physics Society advises against estimating health risks to people from exposures to ionizing radiation that are near or less than natural background levels because statistical uncertainties at these low levels are great.

The average annual equivalent dose¹ from natural background radiation in the United States is about 3 mSv. A person might accumulate an equivalent dose from natural background radiation of about 50 mSv in the first 17 years of life and about 250 mSv during an average 80-year lifetime.

Substantial and convincing scientific data show evidence of health effects following high-dose exposures (many multiples of natural background). However, below levels of about 100 mSv above background from all sources combined, the observed radiation effects in people are not statistically different from zero.

Scientists evaluate and estimate radiation risk using several assumptions that, taken together, may lead to a range of hypothetical health risk estimates for any given exposure scenario.

For radiation protection purposes and for setting radiation exposure limits, current standards and practices are based on the questionable premise that any radiation dose, no matter how small, could result in detrimental

[†] Dose is a term used to express or quantify the amount of radiation a person or object has received. Equivalent dose to an organ or tissue is a quantity derived from the absorbed dose. Equivalent dose is used in radiation protection to relate absorbed dose to the probability of a stochastic radiation effect (cancer induction and hereditary changes) in that organ or tissue. The equivalent dose represents the sum of all of the contributions from radiations of different types multiplied by their respective radiation qualities.

health effects such as cancer or heritable genetic damage. Implicit in this linear no-threshold (LNT) hypothesis is the core assumption that detrimental effects occur proportionately with radiation dose received (NAS/NRC 2006). However, because of statistical uncertainties in biological response at or near background levels, the LNT hypothesis cannot provide reliable projections of future cancer incidence from low-level radiation exposures (NCRP 2001).

Molecular-level radiation effects are nonlinear

Studies show that dose-response relationships are typically nonlinear (Tubiana and Aurengo 2006; Tubiana et al. 2006). Substantial scientific data indicate that the LNT model of radiation effects oversimplifies the relationship between dose and response. Linearity at low dose may be rejected for a number of specific cancers, such as bone cancer, lymphoma, and chronic lymphocytic leukemia. Heritable genetic damage has not been observed in human studies.

Recent low-dose research indicates that biological response mechanisms such as DNA repair, bystander effects, and adaptive response modulate radiation-induced changes at the molecular level. Cellular transformation leading to carcinogenesis by mutation of genetic material appears to be a complicated, multistep process that is not reflected in the LNT model.

Radiogenic health effects have not been consistently demonstrated below 100 mSv

Due to large statistical uncertainties, epidemiological studies have not provided consistent estimates of radiation risk for whole-body equivalent doses less than 100 mSv. Underlying dose-response relationships at molecular levels appear mainly nonlinear. The low incidence of biological effects from exposure to radiation compared to the natural background incidence of the same effects limits the applicability of radiation risk coefficients at organ equivalent doses less than 100 mSv (NCRP 2012).

The references to 100 mSv in this position statement should not be construed as implying that health effects are well established for doses exceeding 100 mSv. Considerable uncertainties remain for stochastic effects of radiation exposure between 100 mSv and 1,000 mSv, depending upon the population exposed, the rate of exposure, the organs and tissues affected, and other variables. In addition, it is worth noting that epidemiological studies generally do not take into account the dose that occupationally or medically exposed persons incur as natural background; thus, the references to 100 mSv in this position statement should generally be interpreted as 100 mSv above natural background dose.

Dose-rate issues

Risk estimates commonly used to predict health effects in exposed individuals or populations are based primarily on epidemiological studies of Japanese atomic bomb survivors and other populations exposed to relatively high doses delivered at high dose rates. Animal, cellular, and molecular studies all demonstrate that at any level of biological organization, the responses following low-dose-rate exposure are less than observed after the same dose delivered at a high dose rate (Dauer et al. 2010). Epidemiological studies have not consistently demonstrated adverse health effects in persons exposed to small (less than 100 mSv) doses protracted over a period of many years.

Collective dose and radiation protection planning

A common approach in many circles, not recommended here, involves extrapolating the calculated risk derived at high doses to low-dose levels. Extrapolation may be convenient for setting radiation protection guidelines. However, when used prospectively to predict future risk to an exposed population, the multiplication of small risk coefficients by large population numbers leads inevitably to unsupportable claims of cancer risk from ionizing radiation (NCRP 1997, 2012).

